9.3.3. Secondary Endpoint Analysis

Part 1 and Part 2

Single-Dose and Steady-State PF-07260437 Pharmacokinetic Analysis

Serum concentrations of PF-07260437 will be summarized descriptively (n, mean, standard deviation, coefficient of variation, median, minimum, maximum, geometric mean, and its associated coefficient of variation) by dose, cycle, day, and nominal time.

Individual participant serum concentration-time data within a dose interval after Cycle 1 Day 1 and Cycle 2 Day 1 will be analyzed using noncompartmental methods to determine single and multiple dose PK parameters.

Single dose PK parameters to be estimated will include the serum C_{max} , T_{max} and AUC_{last} , and as data permit, AUC from time 0 extrapolated to infinity (AUC_{inf}), $t_{1/2}$, clearance (CL/F for SC dosing and CL for IV dosing) and volume (V_z/F for SC dosing and V_{ss} for IV dosing).

Multiple dose PK parameters to be estimated will include $C_{max,ss}$, $T_{max,ss}$, $AUC_{ss,t}$, $C_{min,ss}$, clearance (CL_{ss}/F for SC and CL_{ss} for IV) and as data permit, volume (V_z/F for SC or V_{ss} for IV), $t_{1/2}$, and R_{ac} ($AUC_{ss,t}/AUC_{sd,t}$). The single dose and steady-state PK parameters will be summarized descriptively (n, mean, standard deviation, coefficient of variation, median, minimum, maximum, geometric mean, and its associated coefficient of variation) by dose level and cycle.

Dose normalized AUC_{inf} (AUC_{τ} at steady state) and C_{max} will be plotted against dose (using a logarithmic scale) by cycle. These plots will include individual participant values and the geometric means for each dose.

Analysis of Immunogenicity Data

For the immunogenicity data, the percentage of participants with positive ADA and neutralizing antibodies each will be summarized. For participants with positive ADA or neutralizing antibodies, the magnitude (titer), time of onset, and duration of ADA or neutralizing antibodies response will also be described, if data permit.

Part 2

Efficacy Analysis

Response Evaluable Set will be used for all response-related analyses including ORR, DoR, PFS, and TTP (RECIST). Tumor response will be presented in the form of participant data listings that include, but are not limited to tumor type, tumor response at each visit, and best overall response. OS will be reported on the Full Analysis Set as well as on the mITT.

Data will be summarized (also graphically where appropriate) and listed by expansion cohort.

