1.3.1. Part 1 – Schedule of Assessment - Without Priming

Table 1. Study Schedule of Assessments – Part 1 Without Priming

Visit Identifier Abbreviations used in this table may be found in Appendix 17	Screening	Treatment Period										EOT	4-week Follow- up	90-day Follow- up for irAEs	Notes
		Cycle 1 = 28 days					Cycle ≥2 (28 days)								
Study Day	-28 to -1	1	2	3 ^a	8	15 ^a	22	1	C3D8 ^b	15					
Visit Window (days)		±2			±2	±2	±2	±2	±2	±2		±7		±7	
Additional visit window may be allowed after discussion and agreement between investigator and sponsor.a. End of inpatient observation (PK, ECG, vital signs).b. PK/PD and ECG only.
Informed consent and registration	X														
Informed consent should be obtained prior to any study-specific procedures.At registration, enrollment (randomization) number and dose level will be assigned by Pfizer.
Screen for inclusion/exclusion criteria	X														
See Section 5.1 and 5.2
Demographics	X														

Table 1. Study Schedule of Assessments – Part 1 Without Priming

Visit Identifier Abbreviations used in this table may be found in Appendix 17	Screening	Treatment Period										EOT	4-week Follow- up	90-day Follow- up for irAEs	Notes
		Cycle 1 = 28 days					Cycle ≥2 (28 days)								
Study Day	-28 to -1	1	2	3 ^a	8	15 ^a	22	1	C3D8 ^b	15					
Visit Window (days)		±2			±2	±2	±2	±2	±2	±2		±7		±7	
Medical history and Physical Examination															
Primary cancer diagnosis and prior treatment history	X														
 Additional visit window may be allowed after discussion and agreement between investigator and sponsor. a. End of inpatient observation (PK, ECG, vital signs). b. PK/PD and ECG only.
General medical history	X														
 See Section 8.2 for additional information.
Baseline signs and symptoms	X	X													
 Include date of initial diagnosis and metastatic disease, prior systemic treatments, surgeries, radiotherapy, and recurrence history. Genomic testing if available.
Complete physical examination	X									X					
 Include any concurrent or resolved illness other than the cancer under study. Signs and symptoms experienced within the 28 days prior to first dose.

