1.3.1.1. Part 1 - PK, Immunogenicity, PD, Biomarker, and Biospecimen – Without Priming

Table 2. PK, Immunogenicity, PD, Biomarker, and Biospecimen Schedule of Assessments – Part 1 – Without Priming

Visit Identifier Abbreviations used in this table may be found in Appendix 16	Screenin g	CYCLE 1 - A CYCLE 2 - B CYCLE 3 - C CYCLE \geq 4 - D										EOT	Notes
		Day 1				Day 2	Day 3	Day 8	Day 15			Day 22	
Hours Before/After Dose	Pre (0)	1 hr	4 hr	8 hr	24 hr	48 hr	168 hr	Pre (0)	4 hr	8 hr	168 hr		
Visit Window	-6 hr	+ 10 min	\pm 30 min	\pm 1 hr	\pm 3 hr	\pm 4 hr	\pm 24 hr	-6 hr	\pm 30 min	\pm 1 hr	\pm 24 hr		
PK Assessments													
PK blood sampling		A, B, C, D	A, C (IV only)	A, C	A,C	A	A	A, C	A, C	A	A	X	
 If CRS is suspected, additional PK sample should be collected at time of AE occurrence if not already scheduled. IV only: if actual duration of infusion differs from 1 hour, 1-hour point should be adjusted for the sample to be collected at the end of infusion. See Section 8.4 for additional information.

Table 2. PK, Immunogenicity, PD, Biomarker, and Biospecimen Schedule of Assessments – Part 1 – Without Priming

Visit Identifier Abbreviations used in this table may be found in Appendix 16	Screenin g	CYCLE 1 - A CYCLE 2 - B CYCLE 3 - C CYCLE \geq 4 - D										EOT	Notes	
		Day 1				Day 2	Day 3	Day 8	Day 15		Day 22			
Hours Before/After Dose	Pre (0)	1 hr	4 hr	8 hr	24 hr	48 hr	168 hr	Pre (0)	4 hr	8 hr	168 hr			
Visit Window	-6 hr	+ 10 min	\pm 30 min	\pm 1 hr	\pm 3 hr	\pm 4 hr	\pm 24 hr	-6 hr	\pm 30 min	\pm 1 hr	\pm 24 hr			
Immunogenicity Assessments														
Blood samples for ADA and NAb		A, B, C, D										X	
 From Cycle 4 onwards: collection on Day 1 of every 3 cycles. (C4D1, C7D1, etc.) See Section 8.7 for additional information. 	
Pharmacodynamic and Biomarker Assessments														
Soluble B7-H4 blood sampling		A, B, C, D		A, C	A, C	A	A	A, C	A, C			A	X	
 From Cycle 4 onwards: collection on Day 1 of every 3 cycles. (C4D1, C7D1, etc.) See Section 8.6.6 for additional information.
Serum for cytokine and circulating markers (central lab)		A, B	A	A	A	A	A	A	A	A	A		
 See Section 8.6.3. 	
Blood for Immunophenotyping		A, B				A	A	A	A		A		
 Refer to Section 8.6.4. 	

Table 2. PK, Immunogenicity, PD, Biomarker, and Biospecimen Schedule of Assessments – Part 1 – Without Priming

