1.3.2. Part 1 – Schedule of Assessments - With Priming

Table 3. Study Schedule of Assessments – Part 1 With Priming

Visit Identifier Abbreviations used in this table may be found in Appendix 17	Screening	Treatment Period								EOT	4-week Follow-up	90-day Follow-up for irAEs	Notes
		Cycle 1 =28 days											
Study Day	-28 to -1	1	2 ^a	8	15	16 ^a	22	1	8 ^b	15			
 Additional visit window may be allowed after discussion and agreement between investigator and sponsor.
Visit Window (days)		±2	±2	±2		±2	±2	±2	±2		±7	±7	
a: End of inpatient observation (PK, ECG, vital signs).
 
b: This D8 visit is only applicable for Cycles 2 and 3, whereas, C3D8 is applicable for PK/PD and ECG only.

Informed consent and registration	X												
 Informed consent should be obtained prior to any study-specific procedures. At registration, enrollment (randomization) number and dose level will be assigned by sponsor.
Screen for inclusion/exclusion criteria	X												• See Section 5.1 and 5.2 .
Demographics	X												
Medical history and Physical Examination												See Section 8.2 for additional information	
Primary cancer diagnosis and prior treatment history	X												
 Include date of initial diagnosis and metastatic disease, prior systemic treatments, surgeries, radiotherapy, and recurrence history. Genomic testing if available.
General medical history	X												
 Include any concurrent or resolved illness other than the cancer under study.

PFIZER CONFIDENTIAL

CT02-GSOP Oncology Clinical Protocol Template (01 March 2021)

Table 3. Study Schedule of Assessments – Part 1 With Priming

Visit Identifier Abbreviations used in this table may be found in Appendix 17	Screening	Treatment Period									EOT	4-week Follow- up	90-day Follow- up for irAEs	Notes
		Cycle 1 =28 days												
Study Day	-28 to -1	1	2 ^a	8	15	16 ^a	22	1	8 ^b	15				
 Additional visit window may be allowed after discussion and agreement between investigator and sponsor.
Visit Window (days)		±2		±2	±2		±2	±2	±2	±2		±7	±7	
a: End of inpatient observation (PK, ECG, vital signs).
 
b: This D8 visit is only applicable for Cycles 2 and 3, whereas, C3D8 is applicable for PK/PD and ECG only.

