1.3.2.1. Part 1 - PK, Immunogenicity, PD, Biomarker, and Biospecimen – With Priming

Table 4. PK, Immunogenicity, PD, Biomarker, and Biospecimen Schedule of Assessments – Part 1- With Priming

Visit Identifier Abbreviations used in this table may be found in Appendix 16	Screenin g	CYCLE 1 - A CYCLE 2 - B CYCLE 3 - C CYCLE \geq 4 - D										EOT	Notes		
		Day 1				Da y 2	Day 8	Day 15							
		Pre (0)	1 hr	4 hr	8 hr	24 hr	168 hr	Pre (0)	1 hr	4 hr	8 hr	24 hr	168 hr		
Hours Before/After Dose		-6 hr	+ 10 min	\pm 30 min	\pm 1 hr	\pm 3	\pm 24 hr	-6 hr	\pm 10 min	\pm 30 mi n	\pm 1 hr	\pm 3 hr	\pm 24 hr		
 Pre-dose samples: hours before the immediate dose Post-dose samples: hours after the most recent scheduled dose
PK Assessments															
PK blood sampling		A, B, C, D	A, C (IV only)	A, C	A, C	A	A, C	A, C	A (IV only)	A	A	A	A	X	
 If CRS is suspected, additional PK sample should be collected at time of AE occurrence if not already scheduled IV only: if actual duration of infusion differs from 1 hour, 1-hour point should be adjusted for the sample to be collected at the end of infusion. See Section 8.4 for additional information.
Immunogenicity Assessments															
Blood samples for ADA and NAb		A, B, C, D											X	
 From Cycle 4 onwards: collection on Day 1 of 	

Table 4. PK, Immunogenicity, PD, Biomarker, and Biospecimen Schedule of Assessments – Part 1- With Priming

Visit Identifier Abbreviations used in this table may be found in Appendix 16	Screenin g	CYCLE 1 - A CYCLE 2 - B CYCLE 3 - C CYCLE ≥4 - D										EOT	Notes		
		Day 1				Da y 2	Day 8	Day 15							
		Pre (0)	1 hr	4 hr	8 hr	24 hr	168 hr	Pre (0)	1 hr	4 hr	8 hr	24 hr	168 hr		
Hours Before/After Dose		-6 hr	+ 10 min	± 30 min	±1 hr	±3 hr	±24 hr	-6 hr	± 10 min	± 30 mi n	±1 hr	±3 hr	±24 hr		
 Pre-dose samples: hours before the immediate dose Post-dose samples: hours after the most recent scheduled dose
Visit Window														every 3 cycles. (C4D1, C7D1 etc.) • See Section 8.7 for additional information.	
Pharmacodynamic and Biomarker Samples															
Soluble B7-H4 blood sample		A, B, C, D		A, C	A,C	A	A,C	A,C		A	A	A	A	X	
 From Cycle 4 onwards: collection on Day 1 of every 3 cycles (C4D1, C7D1, etc.) See Section 8.6.6 for additional information.

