PK blood sampling		A, B, C, D	A, C (IV only)	A, C	A, C	A	A	A, C	A	A	A (Priming only)	A	X	
 • Pre-dose samples: hours before the immediate dose • Post-dose samples: hours after the most recent scheduled dose • If CRS is suspected, additional PK sample should be collected at time of AE occurrence if not already scheduled • IV only: if actual duration of infusion differs from 1 hour, 1-hour point should be adjusted for the sample to be collected at the end of infusion. • See Section 8.4 for additional information.
Immunogenicity Assessments														
Blood samples for ADA and NAb		A, B, C, D											X	
 • From Cycle 4 onwards: collection on Day 1 of every 3 cycles. (C4D1, C7D1, etc.) • See Section 8.7 for additional information.
Pharmacodynamic and Biomarker Samples														

Table 6. PK, Immunogenicity, PD, Biomarker, and Biospecimen Schedule of Assessments – With or Without Priming

Visit Identifier Abbreviations used in this table may be found in Appendix 16	Screening	CYCLE 1 - A CYCLE 2 - B CYCLE 3 - C CYCLE ≥4 - D										EOT	Notes	
		Day 1				Day 2	Day 8	Day 15			Day 16	Day 22		
Hours Before/After Dose		Pre (0)	1 hr	4 hr	8 hr	24 hr	168 hr	Pre (0)	4 hr	8 hr	24 hr	168 hr		
Visit Window		-6 hr	+ 10 min	± 30 min	±1 hr	±3 hr	±24 hr	-6 hr	± 30 min	±1 hr	±3 hr	±24 hr		
Soluble B7-H4 blood sample		A, B, C, D					A	A					X	
 From Cycle 4 onwards: collection on Day 1 of every 3 cycles. (C4D1, C7D1, etc.) See Section 8.6.6 for additional information.
Serum for cytokine and circulating markers (central lab)		A, B	A	A	A	A	A	A	A	A	A	A		
 Refer to Section 8.6.3.
Blood sample for immunophenotyping		A, B				A	A	A			A (Priming only)	A		
 Refer to Section 8.6.4.
Optional or mandatory archival tissue	X													
 Optional if de novo tissue sample is provided. Mandatory if a de novo tissue sample is not provided. Refer to Section 8.6.2 for details.
Mandatory or optional de novo	X							B					(X)	
 (x) = Optional

PFIZER CONFIDENTIAL

CT02-GSOP Oncology Clinical Protocol Template (01 March 2021)

Page 65

Table 6. PK, Immunogenicity, PD, Biomarker, and Biospecimen Schedule of Assessments – With or Without Priming

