3. OBJECTIVES, ENDPOINTS, AND ESTIMANDS

Dose Escalation (Part 1):

Objectives	Endpoints	Estimands
Primary		

To assess safety and tolerability at increasing dose levels of PF-07260437 in successive cohorts of participants with locally advanced or metastatic BrCa, OvCa or endometrial cancer.To estimate the MTD and to select RDE.	
Occurrence of DLTs (Section 4.3.6).AEs as characterized by type, frequency, severity (as graded by NCI CTCAE v5 or CRS grading system) timing, seriousness, and relationship to study therapy.Laboratory abnormalities as characterized by type, frequency, severity (graded by NCI CTCAE v5), and timing.	
DLT rate estimated based on data from DLT-evaluable participants during the DLT evaluation period.Incidence of AEs estimated in the safety analysis population during the AE evaluation period.
Secondary		

To assess immune related safety and tolerability at increasing dose levels of PF-07260437 in successive cohorts of participants with locally	
irAEs as characterized by type, frequency, severity (as graded by NCI CTCAE v5) timing, seriousness, and relationship to study therapy.	
N/A

Objectives	Endpoints	Estimands
advanced or metastatic BrCa, OvCa or endometrial cancer.		

 To evaluate the single and multiple dose PK of PF-07260437 as monotherapy. 	
 Pharmacokinetic parameters of PF-07260437 as monotherapy: SD C_{max}, T_{max}, AUC_{last}, and as data permit, $t_{1/2}$, AUC_{inf}, CL/F, and V_z/F. MD (assuming steady state is achieved) $C_{max,ss}$, $T_{max,ss}$, $C_{min,ss}$, $AUC_{ss,T}$, and as data permit, CL_{ss}/F, V_z/F, and R_{ac} ($AUC_{ss,T}/AUC_{sd,T}$). 	
 N/A

 To evaluate immunogenicity of PF-07260437. Tertiary/Exploratory 	
 Incidence and titers of ADA and NAb against PF-07260437. 	
 N/A

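### Multiple-dose PK parameters are to come from the dose interval after Cycle 2 Day 1, where no post-dose PK sample is scheduled; the repeat-dose profile is sampled in Cycle 3.

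*Protocol*

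**What the plan says.** Protocol 9.3.3, under the heading for Part 1 and Part 2, states that individual concentration data "within a dose interval after Cycle 1 Day 1 and Cycle 2 Day 1 will be analyzed using noncompartmental methods". SAP 3.2 and SAP 6.2.2 carry the same sentence. The first interval supplies the single-dose parameters and the second the multiple-dose ones.

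Protocol 3 lists the multiple-dose parameters as Part 1 secondary endpoints, under "MD (assuming steady state is achieved". Cmax,ss, Tmax,ss, Cmin,ss and AUCss,tau are listed outright. CLss/F, Vz/F and Rac are listed there as conditional on the data, although 9.3.3 puts clearance among the unconditional parameters. For Part 2 the PK endpoint is only concentrations at selected times.

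The sampling tables code cycles by letter: "CYCLE 1 - A CYCLE 2 - B CYCLE 3 - C", with D for Cycle 4 onwards. The PK rows read:

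- Table 2, Part 1 without priming: "PK blood sampling A, B, C, D A, C (IV only) A, C A,C A A A, C A, C A A X"
- Table 4, Part 1 with priming (start of row): "PK blood sampling A, B, C, D A, C (IV only) A, C A, C A A, C A, C A (IV only"
- Table 6, Part 2 (start of row): "PK blood sampling A, B, C, D A, C (IV only) A, C A, C A A A, C A A A (Priming only"

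**The concern.** The letter B, for Cycle 2, stands in the first cell of each PK row and nowhere else. That cell is the Day 1 pre-dose sample, which is the trough of the preceding Cycle 1 Day 15 dose and says nothing about the interval that starts at Cycle 2 Day 1. The analysis text and the sampling schedule therefore name different cycles for the repeat-dose profile.

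At stake are listed secondary endpoints. If the sentence is followed literally, Cmax,ss, Tmax,ss and AUCss,tau have no data behind them, and neither do CLss/F, Rac or the planned plot of dose-normalised steady-state AUC. SAP 5.3.4 codes a parameter as not calculated when a participant's data cannot support it, so these entries could all come out that way. If analysts use Cycle 3 instead without a change to the text, they depart from both documents with no record of it. Cmin,ss is less affected, because pre-dose troughs are collected.

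**Working it through.** **Step 1. Count the scheduled PK samples.** Inputs are the PK rows and column headers of Tables 2, 4 and 6. The Day 15 pre-dose sample closes the Day 1 interval at 336 h. The 1 h sample is IV only and is excluded from the SC counts.

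| Table | Cycle 2 (B) | Cycle 3 (C), SC | Post-dose after C2D1 | Post-dose after C3D1 (SC) |
|---|---|---|---|---|
| 2, Part 1 no priming | Day 1 pre-dose | pre-dose, 4, 8, 168 h, Day 15 pre-dose | 0 | 4 |
| 4, Part 1 priming | Day 1 pre-dose | pre-dose, 4, 8, 168 h, Day 15 pre-dose | 0 | 4 |
| 6, Part 2 | Day 1 pre-dose | pre-dose, 4, 8 h, Day 15 pre-dose | 0 | 3 |

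With IV dosing the end-of-infusion sample raises the Cycle 3 counts to 5 and 4. The Cycle 2 count stays at 0.

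**Step 2. Rule out a table-reading error.** As extracted, the Table 2 PK row has 10 time cells against 11 time columns, so the position of its last entries is uncertain. B is still only in its first cell. Table 4 (12 columns, 12 cells) and Table 6 (11 columns, 11 cells) align fully.

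**Step 3. Compare with the visit schedules.** In Table 1 (no priming) the only Day 8 visit after Cycle 1 is C3D8, noted "b. PK/PD and ECG only". Table 3 (priming) has a Day 8 visit in Cycle 2 as well, but its note says "C3D8 is applicable for PK/PD and ECG only", and Table 4 has no Cycle 2 PK sample on that day. The design places the repeat-dose profile in Cycle 3. The only other route to a Cycle 2 post-dose sample is one triggered by suspected CRS, which would not give a profile.

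**Step 4. How near steady state is each interval?** This is an illustration and assumes one-compartment kinetics without priming. Cycle 2 Day 1 is the third Q2W dose and Cycle 3 Day 1 the fifth. The half-life is 15 days as stated in Protocol 2.2.2, or ln 2 × 84 / 0.2 = 291 h = 12.1 days from the clearance and volume given there.

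With instantaneous input, the fraction of steady-state AUC at dose n is 1 − r^n, where r = 2^(−14/t½):

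- 15 days: r = 0.524; dose 3 gives 0.856, dose 5 gives 0.961.
- 12.1 days: r = 0.449; dose 3 gives 0.909, dose 5 gives 0.982.

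With slow SC absorption, further assumptions are 70 kg, V = 5.88 L, F = 0.7 and a 100 µg dose. The absorption rate ka is solved so that the single-dose Cmax equals the 9.2 ng/mL of Protocol 4.3.1.1, which gives 0.0190 per h (15 days) or 0.0236 per h (12.1 days). Dose 3 then gives 0.840 / 0.899, and dose 5 gives 0.956 / 0.980.

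**Step 5. What would Cycle 3 sampling miss?** Same absorption model, samples at 0, 4, 8, 168 and 336 h after Cycle 3 Day 1:

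| | t½ 15 d | t½ 12.1 d |
|---|---|---|
| True Cmax (ng/mL), at | 20.07, 93 h | 17.50, 81 h |
| Highest sampled value | 18.79 | 15.57 |
| Error in Cmax,ss | −6.4% | −11.0% |
| Error in linear-trapezoid AUCss,tau | −6.0% | −7.9% |

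The modelled peak falls between the 8 h and 168 h samples, so only 168 h and 336 h lie on the declining part of the curve.

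**The case against.** The mismatch itself is hard to dispute, so the case on the other side concerns its weight.

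- **It is probably a wrong cycle number.** The tables make the intended cycle evident, every needed sample is scheduled, the output is descriptive and no hypothesis is tested. Protocol 9.3.6.2 also permits compartmental modelling that could use the Cycle 3 data. This stands as a limit on severity. That modelling is optional, however, and may be reported separately, so it does not deliver the listed endpoints.
- **The documents allow correction.** Protocol 9 lets the SAP modify the protocol, but the SAP repeats the Cycle 2 wording twice. Protocol 8.4 lets time points be added and archived in study files without an amendment, so added Cycle 2 samples might not be visible here. The most that can be said is that neither document shows any.
- **The not-calculated coding is one reading.** SAP 5.3.4 refers to a participant's concentration data in general, and Cycle 3 concentrations are among them. That outcome follows only if the Cycle 2 sentence is applied strictly.
- **Cycle 3 sampling is sparse too.** This stands. AUC bias would carry into CLss/F and Rac, and a multiple-dose half-life or terminal volume would rest on two points. It is a caveat on the fix, since the alternative as written is no post-dose samples at all.

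**Conclusion.** The concern holds. The interval named for the multiple-dose noncompartmental analysis has 0 scheduled post-dose samples in all three sampling tables, against 4 (Part 1) and 3 (Part 2) for SC dosing after Cycle 3 Day 1. Cmax,ss, Tmax,ss, AUCss,tau, CLss/F and Rac cannot be obtained from it. This rests on a count and needs no modelling assumption.

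The practical effect falls on the Part 1 secondary PK endpoint, because Part 2 asks only for concentrations. It should be fixed, but it does not threaten the study: the data needed are already planned, and only the analysis text is wrong. The steady-state fractions and bias figures are illustrative and depend on the one-compartment model and the inputs listed above.

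**What to change.** In Protocol 9.3.3, SAP 3.2 and SAP 6.2.2, replace Cycle 2 Day 1 with Cycle 3 Day 1 for Part 1, and state that Part 2 PK is limited to concentration summaries. Add a sentence that, with no Cycle 3 sample between 8 h and 168 h, Cmax,ss and Tmax,ss will be coarse, AUCss,tau may be somewhat low, and terminal-phase estimates will be weak. The cost is one phrase in the protocol, two in the SAP and a few sentences, with no new draws.

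The alternative is to keep Cycle 2 Day 1 and schedule post-dose Cycle 2 samples. That costs extra draws and gives an interval further from steady state.

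A separate, smaller point can be settled in the same edit. In primed participants the Cycle 1 Day 1 dose is the priming dose, so the plan should say whether Rac uses dose-normalised AUCs over matching intervals or is not reported for them.
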